#### **4. Study Design and Methods**

##### **a. Study overview**

Participants will be children aged 6 months to 12 years and their parents. Participants will receive children's products or toys to play with during an hour play session. Based on the manufacturer's suggested age, some products will be geared towards children who are younger, some will be geared toward children their own age, and others will be aimed at older children. Each child will first play alone and then play with a parent. Different sets of toys will be presented when children switch from playing alone to playing in a dyad. The play sessions will be videorecorded. Video records will subsequently be scored for children's play with the toys.

Participation in this project will take roughly 1-2 hours for the play session of the visit and approximately 1 additional hour for the parent to complete accompanying relevant questionnaires, which can be done at home. Participation in the study requires one visit to the CFRS lab.

This research is social and behavioral in nature, and the visits are considered outpatient. Participants will be tested at the CFRS laboratory in Bethesda, MD.

Subjects who participate in this study are not required to participate in other protocols.

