To decrease the burden on parents and their children, reduce unplanned missingness, and increase data quality, we are using a 3-form planned missingness design. Because of this design, parents and their children will only have to play with toys from 6 of the 9 categories.

Parents and their children will be offered to take a break from playing approximately every 15 minutes during the toy play session in the event that they are tired of playing with the toys. In addition, to ease frustration that can occur when transitioning from one toy type to the next, we will give children and their parents a couple of minutes notice before the transition occurs.

All play sessions will be video recorded.

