#### Video behavior coding

Video records of the toy play session will be scored for certain qualitative and quantitative behaviors, including, *but not limited to*:

- The Toy Quality Scale (TQS): Qualities of the toy itself (i.e., are there moving parts, does the toy make noise, how soft is the toy? Is it a branded toy with a licensed character on it?). This coding system is being developed in CFRS.
- Parts and features of toys used by the child.
- Duration of time child spends with each toy.
- When playing with parent, how often, in what way, and for how long does the child solicit the parent’s involvement? How often, in what way, and for how long does the parent solicit the child’s involvement?
- Level of Play Complexity (taken from Bornstein et al., 1996; Cote & Bornstein, 2009, Suizzo & Bornstein, 2006):
  - (0) *default* (no play);
  - (1) *unitary functional activity* (e.g., throw the ball);
  - (2) *inappropriate combinatorial activity* (e.g., put the ball into a teacup): Was the toy used as intended or features of toy fully exploited?
  - (3) *appropriate combinatorial activity* (e.g., put the cup on the saucer);
  - (4) *transitional play* (e.g., put the telephone to the ear without speaking);
  - (5) *self-directed pretense* (e.g., drink from a cup);
  - (6) *other-directed pretense* (e.g., pretend to feed the doll);
  - (7) *sequential pretense* (e.g., dial and speak into the telephone); and
  - (8) *substitution pretense* (e.g., pretend the block is a telephone receiver and speak into it).

Note that all of these procedures described above are solely for research purposes, not for medical or clinical evaluation or treatment. Radiation is not used in this study.

There are no follow-up visits associated with this study. The study has no relations to any other existing protocol.

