### **b. Secondary outcome measures**

Our other secondary outcome measures include the following:

- Parts and features of toys used by the child
- Duration of time child spends with each toy
- Child preference for the toys based on child-report (smiley face Likert scale)
- Number of times and duration of time the child solicits the parent's or friend's involvement during play

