## **10. Statistical Analysis**

### **a. Analysis of data/ study outcomes**

For our primary outcome measure, our independent variables will be the age group for which the toy is aimed (younger vs. age-appropriate vs. older; within-subject) and the age group of the child (6 groups; between-subject), and our dependent variables will be the video-coded measures of play. The statistical methodology that we will use to analyze this question is a repeated-measures ANCOVA with up to five covariates. Our five covariates include the following: (1) toy characteristics, (2) child temperament, (3) family socioeconomic status, (4) child preferences for the toy, and (5) parenting knowledge.

For our secondary outcome of interest (how children play alone vs. with parent), we will conduct another repeated-measures ANCOVA with condition (alone vs. with parent) and designated toy age (younger vs. age-appropriate vs. older) as within-subject factors and child age (6 groups) as a between-subject factor. Again, our dependent variables will be the video-coded measures of play. We will also use the same five covariates mentioned above: (1) toy characteristics, (2) child temperament, (3) family socioeconomic status, (4) child preferences for the toys, and (5) parenting knowledge.

Both of the repeated-measures ANCOVA designs will also be employed when we examine the dependent variables of secondary interest noted in section 9b, such as parts and features of toys used by the child, duration of time child spends with each toy, child preference for the toys based on child-report (smiley face Likert scale), and the number of times and duration of time the child solicits the parent's involvement during play. The independent variables mentioned above would remain the same.

We do not have any planned interim analysis. Our criteria for significance is alpha = .05. Due to the protocol's design, unplanned missingness will be low. Missing data procedures, such as Full Information Maximum Likelihood and Multiple Imputation, will be used.

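### Section 10a applies the solo-versus-parent model to child solicitation, which has a coding rule only for parent play; and with solo play always first, the condition effect is partner plus phase order

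*Combined protocol and SAP*

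**What the plan says.** Section 10a sets out two repeated-measures ANCOVAs. The first has toy age (three levels, within child) and child age group (six groups, between children). The second adds play condition, solo or with the parent, as another within-child factor. It serves secondary objective 1 in Section 2b, the effect of play group type.

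For the secondary outcomes, Section 10a says "Both of the repeated-measures ANCOVA designs will also be employed when we examine the dependent variables of secondary interest noted in section 9b". The outcomes it then lists include "the number of times and duration of time the child solicits" the parent's involvement, and it adds: "The independent variables mentioned above would remain the same". On incomplete data it says: "Missing data procedures, such as Full Information Maximum Likelihood and Multiple Imputation, will be used".

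The coding rule is in Section 4c, Video behavior coding: "When playing with parent, how often, in what way, and for how long does the child solicit" the parent's involvement. That list is expressly not exhaustive. Section 9b is broader, "Number of times and duration of time the child solicits the parent's or friend's involvement during play", although no friend takes part in this design; the Précis likewise refers only to play in general. Section 4c also says "All play sessions will be video recorded", so solo play is on film.

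On order, Section 4a says "Each child will first play alone and then play with a parent". The Précis and Section 4c agree. The toy sets change at the switch (Sections 4a and 4c). The counterbalancing in the Précis and Section 4c concerns which of three toys per category a child receives. The five covariates in Section 10a include toy characteristics and the child's toy preference; none is phase or order.

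**The concern.** There are two separate problems in the same model.

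**Solicitation.** Followed literally, Section 10a compares solicitation in solo play with solicitation in parent play, but the only written rule yields values for parent play alone. The analysis would then either report a condition effect produced by the scoring or have no solo level to compare.

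**Condition main effect.** Secondary objective 1 asks how the play group affects play. With one fixed order, warm-up, tiredness or familiarity with the room moves the contrast exactly as a partner effect would. A significant result could be order, and a real partner effect could be cancelled. Nothing in the plan limits what will be attributed to the parent.

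**Working it through.** **The plan's own figure.** Section 10b says 360 dyads suffice for f = 0.25 at power 0.80 and alpha 0.05. In a conservative version, with noncentrality f²N = 0.0625 × 360 = 22.5 and five covariate degrees of freedom, power is 0.997 for condition and 0.921 for a 10-df interaction. The statement is confirmed, but it does not bear on either problem: a larger sample removes neither.

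**Solicitation, solo play scored zero.** Let P be a child's score in parent play.

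- Parent minus solo = P − 0 = P. The condition test therefore only asks whether the mean of P exceeds zero.
- The average over conditions = (P + 0)/2 = P/2. F ratios do not change when scores are multiplied by a constant, so the toy-age and child-age tests, and their interactions with condition, only repeat the parent-phase tests.
- Illustration, with rates assumed because the documents give none: for Poisson counts with a mean of 0.02 per child (0.02 × 360, about 7 events in the whole study), condition is significant with probability about 0.93 in simulation.

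**Solicitation, solo play uncoded.** Each child has 2 × 3 = 6 cells, and the 3 solo cells are empty for everyone: 3 × 360 = 1,080 of 2,160 values. A complete-case analysis keeps no child. Full information maximum likelihood works from observed data, and a mean observed for no child is not identified; multiple imputation likewise has no solo value to model. This differs from the planned missingness in Section 4c, where children receive 6 of the 9 toy categories.

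**Condition main effect.** The estimated contrast is

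parent − solo = partner effect + order effect (+ any toy-set difference between phases).

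All children have the same order, so these terms cannot be separated. For size, treat it as one paired contrast without covariates. SD means the SD of a child's score within a phase, and rho is the correlation of the two phase scores. Both rho and the shift are assumed.

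SE = √(2(1 − rho)/360), which is 0.0527 SD at rho = 0.5 and 0.0667 SD at rho = 0.2.

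Probability that condition is significant (noncentral t, alpha 0.05) when the partner effect is zero:

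| Order shift (SD) | rho = 0.5 | rho = 0.2 |
|---|---|---|
| 0.10 | 0.47 | 0.32 |
| 0.15 | 0.81 | 0.61 |
| 0.20 | 0.97 | 0.85 |

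Masking works the same way. A partner effect of +0.20 SD with an order effect of −0.20 SD gives an estimate of 0.00 and rejection in 5.7% of simulations (rho = 0.5).

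**Primary contrast.** Section 4c presents the target toy together with the younger and older toys from its category. Toy age is thus compared within a phase, and a shift common to all toys in that phase cancels. A uniform shift also cancels from the interactions of condition with child age and toy age; those are affected only if the order effect itself differs by child age or toy age.

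**The case against.** **Solo solicitation may be observable.** The Précis and Section 9b do not confine solicitation to the parent phase, the coding list in Section 4c is open, solo play is filmed, and nothing says the parent is out of reach. If children can call on the parent during solo play, the comparison is meaningful. This stands in part: a reader might infer that Section 10a is certainly an analysis error, or that no solo data can exist, and the documents do not support either. But an open list is not a rule, and the one rule written down covers parent play only.

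**Toy differences are handled.** Toys are counterbalanced within category, and toy characteristics and preference are covariates. This too stands in part. A reader might infer that toy sets are unbalanced across phases; the documents do not say that, but nor do they say the sets are balanced. Preference is asked only of children over 4, and no covariate can stand in for order.

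**Fixed order is a legitimate choice.** Section 1 describes parents prompting more complex play, which could carry over into later solo play, and breaks about every 15 minutes address tiredness. This stands. A reader might infer that the order must be counterbalanced; the documents do not show that, because counterbalancing would exchange an order effect for possible carry-over. What remains is that the conclusion is not limited to what a fixed order can show.

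**Conclusion.** Both points hold as corrections to the analysis plan.

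1. Under the only written coding rule, the condition test for solicitation is either trivial or not identifiable. This follows from the text and needs no assumed number.
2. The condition main effect for secondary objective 1 is fully aliased with phase order. That is certain from the design; its size is not. The probabilities of 0.47 to 0.97 (rho = 0.5) and 0.32 to 0.85 (rho = 0.2) illustrate order shifts of 0.10 to 0.20 SD. They rest on assumed shifts and correlations and are not evidence that a shift exists.

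A reader might infer that the primary toy-age result is compromised. It is not by itself biased by phase order. The matter concerns a secondary objective and one of the listed secondary outcomes. It should be corrected because the corrections are cheap and specific.

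**What to change.** **Solicitation (Section 10a).** State that child solicitation of the parent will be analysed in the parent-play phase only, by toy age and child age group, without the condition factor. Only if solo-phase solicitation is truly intended, add a coding rule for it in Section 4c, say whether the parent is present during solo play, and reconcile Sections 4c, 9b and 10a. Section 9b's mention of a friend should be reconciled with the design in either case.

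**Condition contrast (Sections 2b and 10a).** State that all children play alone first, that the contrast estimates partner plus phase order, and that it will not be attributed to the parent alone. Say whether toy sets are rotated across the solo and parent phases, and rotate them if they are not.

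**Cost.** The text changes cost nothing in sample size or session length, and restricting solicitation to parent play loses nothing that the present coding rule could supply. Rotating toy sets alters only the assignment list. Counterbalancing phase order remains an optional trade-off because of carry-over.

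### Section 10a applies both RM-ANCOVAs to child preference while keeping child preference as a covariate, so depending on the covariate's form either every effect or only the age-band effect on that outcome is lost

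*Combined protocol and SAP*

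**What the plan says.** Section 10a defines two models.

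- The primary model has toy age (within child) and child age band (between children) as factors. It is described as a "repeated-measures ANCOVA with up to five covariates", and its covariate list ends "4) child preferences for the toy, and (5) parenting knowledge".
- The second model adds play condition (alone or with a parent) as a within-child factor. For this model the text is firm: "We will also use the same five covariates mentioned above". Child preference is again number (4).

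Section 10a then carries both models over to the secondary outcomes: "Both of the repeated-measures ANCOVA designs will also be employed when we examine the dependent variables of secondary interest noted in section 9b". Among the dependent variables it names is "child preference for the toys based on child-report (smiley face Likert scale"), which matches the entry in section 9b. The paragraph closes with "The independent variables mentioned above would remain the same". It does not say that any covariate is dropped for any outcome.

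Section 10b repeats the full list of five covariates for both research questions. Section 4c, under the child questions, describes the only child-preference measure in the protocol: children over 4 rate how much they liked each toy on a smiley-face scale.

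**The concern.** Followed literally, the plan puts the same ratings on both sides of the model when preference is the outcome. Adjusting a variable for itself removes the variation that the factors are meant to explain.

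Preference is the only section 9b outcome that the child reports directly. Two questions depend on it: whether children prefer toys aimed at their own age to toys aimed at adjacent ages, and whether that preference changes with age band. Both bear on the primary objective in section 2a of sorting toys into age groups. One or both cannot be answered if the covariate stays in.

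This is a different matter from whether preference is a sensible covariate for the video-coded outcomes, and from how many children can supply a rating.

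**Working it through.** **Inputs from the documents.** 360 dyads, 6 age bands, 3 toy ages, 5 covariates, f = 0.25, alpha = 0.05 (section 10b); covariate (4) and the carry-over to section 9b outcomes (section 10a); one smiley rating per toy (section 4c).

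**Inputs assumed.** The documents give no preference data, so an illustrative set was generated: 3 age groups × 60 children × 3 toy ages, child SD 0.6, residual SD 0.7. Three groups are used because ratings come only from children over 4. The zeros below are algebra and do not depend on these values.

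**1. The plan's own figure.** Take the conservative noncentrality λ = N f² = 360 × 0.25² = 22.5, with between-child error df 360 − 6 − 5 = 349. Power is 0.97 for age band (df 5), 0.99 for toy age (df 2) and 0.92 to 0.93 for their interaction (df 10). The repeated-measures formula with 3 measures gives 0.98 or more for correlations from 0 to 0.9. The correlation is not stated, so 0.80 is not reproduced exactly, but 360 is sufficient for these effects. This point does not disturb that.

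**2. Preference entered per toy.** For child i in age group g and toy age j, the model is

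Y_ij = μ + α_g + τ_j + (ατ)_gj + β X_ij + e_ij, with X_ij = Y_ij.

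Setting β = 1 and every other term to 0 fits exactly, so the residual sum of squares is 0 and each F is 0/0. Adding play condition adds terms but leaves that solution unchanged. In the illustrative data the covariate slope was 1, every toy-age, age-group and interaction coefficient was 0, and the residual sum of squares was about 1e-26, which is rounding error.

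**3. Preference entered as the child's average.** A repeated-measures ANCOVA then splits into two parts.

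- Between children: Ȳ_i = μ + α_g + β(X_i − X̄) + e_i, with X_i = Ȳ_i. Again β = 1, α_g = 0 and the residual is 0.
- Within children: a contrast C_i = Σ c_j Y_ij with Σ c_j = 0 is regressed on age group and X_i. The contrast is not a function of the average, so its effects stay estimable.

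Results with the average centred on the grand mean:

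| Effect on preference | Without the covariate | With the child's average as covariate |
|---|---|---|
| Age group, two coefficients | −0.2305 and 0.0829; residual SS 83.53 | 0 and 0; residual SS 0 |
| Toy age, second level minus first | 0.365 (t 5.01) | 0.365 (t 5.00) |
| Toy age, third level minus mean of the first two | 0.103 (t 1.57) | 0.103 (t 1.56) |
| Toy age × age group, first coefficient of each contrast | −0.079; −0.168 | −0.073; −0.160 |

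Play condition in the second model is also a within-child contrast. The same reasoning applies to it if the average is taken over both conditions; this was not simulated separately.

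**4. Effect of removing covariate (4).** Between-child error df goes from 360 − 6 − 5 = 349 to 360 − 6 − 4 = 350. Fewer children supply ratings, but the change is still one degree of freedom, and all effects on preference become estimable.

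**The case against.** Five arguments can be made on the other side.

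- **The primary model permits fewer than five covariates.** This is true: the wording is "repeated-measures ANCOVA with up to five covariates", so dropping preference would not breach that model. But no rule says when a covariate is dropped, and the second model has no such latitude.
- **The closing sentence carries over only independent variables.** Section 10a uses that term for toy age and child age and lists covariates separately, so "The independent variables mentioned above would remain the same" is not evidence that the covariates carry over. This stands. The carry-over rests instead on the sentence that re-employs both designs, which were defined with their covariates.
- **Covariate and outcome need not be the same number.** The covariate is named without an instrument or a level. This stands as to level, and it is why the conclusion has two branches. No second child-preference measure is defined, however, so under either form in the working the covariate comes from the same ratings.
- **The harm would show itself.** A slope of 1 with no residual would be noticed, so a misleading result is unlikely to be published. That is fair, but the remedy would then be chosen after the data were seen.
- **Only one of four secondary outcomes is touched.** This is correct.

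A reader might also infer that the whole preference analysis is bound to be lost. The documents do not support that. It requires the rating to enter toy by toy. The singular wording of covariate (4) in the primary model and the per-toy collection of ratings lean that way, but neither settles it. One value per child is the usual covariate form in a classical repeated-measures ANCOVA, and under that form the toy-age comparison survives.

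**Conclusion.** The specification is wrong as written: child preference is both an outcome and a covariate of the models applied to it, and nothing exempts it. The size depends on a detail the plan leaves open.

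- Per-toy covariate: all toy-age, age-band and condition effects on preference are zero with no residual, and F is undefined.
- Child-average covariate: the between-child age-band effect is lost. Toy age and its interaction with age band remain estimable and almost unchanged.

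The age-band comparison therefore fails under both forms, and the own-age versus adjacent-age comparison fails under one. This assumes that the smiley rating supplies both the outcome and the covariate, as the only child-preference measure defined. The near-unchanged toy-age figures come from assumed, balanced data with a grand-mean-centred covariate.

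It would be wrong to extend the point to the primary outcomes, the other section 9b outcomes or the sample size: none of them is adjusted for itself, and the section 10b statement stands. This is a definite error in one secondary analysis that should be corrected, not a threat to the study's main result.

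**What to change.** Add one sentence to section 10a: when child preference is the dependent variable, covariate (4) is omitted from both repeated-measures ANCOVAs, leaving toy characteristics, child temperament, family socioeconomic status and parenting knowledge. A general rule that no outcome serves as its own covariate would achieve the same.

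It would also help to say whether preference enters per toy or as a child average in the models for the other outcomes, although this point is cured without it.

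The cost is the added text. No data, participants or changes to the other outcomes' models are needed.

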**Total requested accrual**

(0) Patients

(720) Healthy Volunteers

	Child participants (ages 6mos-12 years)	Accompanying parents (at least 18 years of age)
6-11 mos	60	60
12-18 mos (1-1.5 years)	60	60
19-35 mos (1.5-2 years)	60	60
36-71 mos (3-5 years)	60	60
72-107 mos (6-8 years)	60	60
108-144 mos (9-12 years)	60	60
	360	360

Total Number of participants (360 + 360) = **720**

**Project Uses Ionizing Radiation:**  No  Yes (attach RSC/RDRC documentation)

Medically-indicated only

Research-related only

Both

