## **9. Outcome Measures**

### **a. Primary outcome measures**

The primary study outcomes are the video-coded measures of age-appropriateness and play complexity. We will examine differences in the mean scores of play among toys from the three age groups that are chronologically adjacent (i.e., the differences in outcomes for a given age group with the age-appropriate toy in comparison with toys from the same toy category just below and just above that age group).

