### **b. Power analysis**

For our primary research question, a power analysis revealed that 360 parent child dyads split across 6 age groups and 3 within-subject designated toy ages (younger vs. age-appropriate vs. older) is sufficient to detect a medium effect ( $f = .25$ ) for between-subjects and within-subjects effects and their interactions in a RM-ANCOVA with 5 covariates (power = .80 and alpha = .05).

For our secondary research question, a power analysis revealed that 360 parent child dyads split across 6 between-subject age groups, 2 within-subject conditions (alone vs. with parent), and 3 within-subject designated toy ages (younger vs. age-appropriate vs. older) is sufficient to detect a medium effect ( $f = .25$ ) for within- and between-subject effects and their interactions in a RM-ANCOVA with 5 covariates (power = .80 and alpha = .05).

For both our primary and secondary research questions, our five covariates include the following: (1) toy characteristics, (2) child temperament, (3) family socioeconomic status, (4) child preferences for the toys, and (5) parenting knowledge. Subject dropouts will be replaced with other comparable subjects who complete the protocol.

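### Two unranked primary outcomes are each tested at .05 with no multiplicity control; Holm across the two would cost the omnibus tests little, but the within-band contrasts need their own stated rule.

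*Combined protocol and SAP*

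**What the plan says.** Section 9a states: "The primary study outcomes are the video-coded measures of age-appropriateness and play complexity". Neither outcome is placed above the other. The same section describes the comparison of interest as "the differences in outcomes for a given age group with the age-appropriate toy in comparison with toys from the same toy category" aimed just below and just above that age group.

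Section 10a analyses the primary outcomes by repeated-measures ANCOVA, with toy age (three levels, within child) and child age group (six levels, between children). It uses the same models for the secondary outcomes in 9b and closes with "Our criteria for significance is alpha = .05".

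Section 10b bases power on "360 parent child dyads split across 6 age groups and 3 within-subject designated toy ages" and calls this "sufficient to detect a medium effect ( $f = .25$ ) for between-subjects and within-subjects effects and their interactions", with five covariates, power .80 and alpha .05. No adjustment, gatekeeping order or single decisive effect is given, and 10a does not say how the age-specific comparisons in 9a will be tested.

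**The concern.** With two co-equal primary outcomes and three powered effects on each (toy age, child age, their interaction), six omnibus F tests can each be declared significant at .05. The plan does not say whether success means one outcome or both, or which effect decides. A significant result on either outcome could therefore be presented as the primary finding, at an overall error rate above the stated 5%.

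The primary objective in section 2a is to place toys in age groups by comparing play with a target toy against play with toys for the adjacent ages. The results are meant to inform revision of the CPSC age-determination guidelines. The error rate attached to those comparisons should be fixed before the data are seen.

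**Working it through.** **Inputs from the documents.** Two primary outcomes (9a). Three effects per outcome, alpha .05, f = .25, power .80, N = 360, six age groups, m = 3 toy ages, five covariates (10a, 10b). Sixty dyads per age group (accrual table).

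**Assumptions.** The documents give no within-child correlation ρ, sphericity factor ε or effect-size convention. I use ρ = .5 to .9 for the main figures and also check ρ = 0 and ε = .5.

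**The plan's own figure.** By noncentral F at alpha .05, the N needed for power .80 is:
- child age: 143 (ρ = .5) or 198 (ρ = .9)
- interaction: 49 (ρ = .5, ε = 1) to 143 (ρ = 0, ε = .5)
- interaction as a plain fixed-effects ANCOVA, the most conservative convention tried: 270

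No variant returns exactly 360. The plan claims only sufficiency, and that claim is correct under every variant.

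**Error rate, all nulls true and tests independent.**
- Two outcomes, one effect: 1 − .95² = 9.75%
- Two outcomes, three effects: 1 − .95⁶ = 26.5%, and at most 6 × .05 = 30% under any dependence

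**Omnibus power after Holm over two outcomes.** Holm tests the smaller p-value at .05/2 = .025 and the other at .05, so power at .025 is the worst case.

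Child age: df 5 and 360 − 6 − 5 = 349; λ = N·m·f²/(1 + (m − 1)ρ) = 67.5/(1 + 2ρ).

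Toy age and interaction: λ = 67.5·ε/(1 − ρ); numerator df 2ε and 10ε, error df 2 × 349 × ε.

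Conservative convention for the interaction: λ = N·f² = 22.5; df 10 and 360 − 18 − 5 = 337.

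| Effect | λ | Power at .05 | Power at .025 |
|---|---|---|---|
| Child age, ρ = .5 | 33.75 | .998 | .996 |
| Child age, ρ = .9 | 24.11 | .980 | .961 |
| Interaction, ρ = .5, ε = 1 | 135 | >.99 | >.99 |
| Interaction, ρ = 0, ε = .5 | 33.75 | .998 | .996 |
| Interaction, conservative | 22.5 | .921 | .871 |

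Toy age stays above .99 at .025 under the repeated-measures formula for every ρ ≥ 0 and ε ≥ .5.

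**All six tests as one family.** At .05/6 = .0083, child-age power is .987 (ρ = .5) or .916 (ρ = .9). The conservative interaction falls to .770, below the planned .80.

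**Age-specific contrasts.** Two per band × six bands = 12 per outcome, 24 for both. By paired t with n = 60, the d_z (mean difference over the SD of the differences) detectable with 80% power is:

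| Threshold | Detectable d_z |
|---|---|
| .05 | .368 |
| .05/12 | .496 |
| .05/24 | .527 |

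At a true d_z of .368, power falls from .80 to .45 at .05/12. With f = .25 and ρ = .5, linear means across the three toy ages give an adjacent difference of .31 SD, and power falls from .645 to .212 at .05/24. If the target toy differs equally from both neighbours (.53 SD), it falls from .981 to .806.

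**The case against.** **The error rates are upper-end figures.** They assume independence and that every null is true. Section 1 says play grows more complex with age, so a true child-age null for play complexity is implausible. Dropping that test leaves five and 1 − .95⁵ = 22.6%. This shrinks the figure but leaves the gap.

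**The cost is larger than the omnibus figures suggest.** A reader might infer from the spare omnibus power that control is almost free throughout. The contrasts in bands of 60 show otherwise. Effective N can also be lower: each child sees six of nine toy categories, so a single-category analysis has about 360 × 6/9 = 240 children. There, child-age power at .025 is .944 (ρ = .5) or .818 (ρ = .9), and the conservative interaction is .637, having been only .738 at .05. The model in 10a does not split by category, so this limits the power claim without overturning it for the planned analysis.

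**The plan does not specify 12 or 24 contrasts at .05.** A reader might quote 1 − .95¹² = 46% or 1 − .95²⁴ = 71% as the plan's error rate. But 10a is silent on follow-up tests, and the two contrasts in a band share the target toy, so they are not independent. What stands is that the rule is missing.

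**Consequences.** A reader might infer that a chance difference is likely to be acted on. The documents say that the findings inform the guidelines, not that revisions follow individual p-values.

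**Coding of age-appropriateness.** The coding list in 4c has no item of that name, which might suggest the outcome is unmeasured. The list is expressly not exhaustive, and level 2 of the complexity scale asks about intended use. The documents do not support more than that the scale is unstated.

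**Conclusion.** The point holds in limited form. Two unranked primary outcomes are tested at .05 with no multiplicity control. The familywise error is 9.75% per effect and 26.5% over all six omnibus tests, given independence and all nulls true.

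Holm over the two outcomes keeps omnibus power at .96 or higher for ρ = .5 to .9 under the repeated-measures formula, and at .87 for the interaction under the most conservative convention. These figures rest on ρ, ε and a convention that the documents do not state, and on all 360 dyads contributing.

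The low cost does not extend to the age-specific contrasts, where full control takes the detectable d_z from .37 to about .50 or .53. Nor does the gap require the 9b outcomes to be relabelled as descriptive: 10a plans tests for them, and downgrading those would be a preference.

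**What to change.** In 10a, do one of the following:
- **Keep both primary outcomes** and apply Holm across them for each omnibus effect (.025, then .05). The cost is the power loss tabulated above.
- **Name play complexity as the single primary outcome**, tested at .05. This costs no power, but age-appropriateness, the concept in the primary objective, then supports rather than decides.

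Either option controls error within one effect. Across three effects the rate could still reach 1 − .95³ = 14.3% if independent and all nulls are true, so 10a should also name the decisive effect or say that control is per effect. Holm over all six tests is available at the .05/6 cost shown above.

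Add a sentence defining the family of target-versus-younger and target-versus-older contrasts (12 for one outcome, 24 for both), the adjustment used, and the d_z detectable with 60 children per band. Section 10b should state the ρ, ε and effect-size convention assumed. These are text changes, with no extra data or recruitment. The real cost is lower sensitivity in the contrasts, which should be accepted openly in advance.
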